## 4.4 Definition/Derivation of Safety Variables

### 4.4.1 MedDRA Preferred Terms or SMQs to Be Used to Define The Events of Interest

The events of interest will be defined using MedDRA preferred terms or SMQs as follows.

- Wound healing events/disorders or complications

MedDRA Preferred term
Abdominal wound dehiscence
Culture wound positive
Debridement
Fungating wound
Incision site abscess
Incision site blister
Incision site cellulitis
Incision site complication
Incision site erythema
Incision site haematoma
Incision site haemorrhage
Incision site infection
Incision site oedema
Incision site pain
Incision site pruritus
Incisional drainage
Inflammation of wound
Post procedural cellulitis
Post procedural infection
Postoperative stitch sinus

*Postoperative wound complication*

*Postoperative wound infection*

*Promotion of wound healing*

*Stitch abscess*

*Suture related complication*

*Suture rupture*

*Wound abscess*

*Wound complication*

*Wound contamination*

*Wound decomposition*

*Wound dehiscence*

*Wound drainage*

*Wound evisceration*

*Wound haemorrhage*

*Wound infection*

*Wound infection bacterial*

*Wound infection fungal*

*Wound infection helminthic*

*Wound infection pseudomonas*

*Wound infection staphylococcal*

*Wound infection viral*

*Wound necrosis*

*Wound secretion*

*Wound sepsis*

*Wound treatment*

High level term

*Healing abnormal NEC*

Following preferred terms under the high level term “*Healing abnormal NEC*” will also be searched:

*Excessive granulation tissue*

*Impaired healing*

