A recent analysis (Shihab 2012) from study CRAD001A2309 has shown that an exposure above 3 ng/mL is adequate in reducing the risk of tBPAR. Moreover, lowest rates of renal dysfunction (defined as poor renal function [estimated GFR, serum creatinine] or proteinuria), wound healing events, peripheral edema, new-onset diabetes mellitus, hypercholesterolemia and hypertriglyceridemia were generally observed with everolimus trough concentration in the range 3–8 ng/mL and CsA levels of <100 ng/mL.

Two short-term studies conducted in the US have evaluated the de novo use of everolimus in combination with tacrolimus. CRAD001AUS01 was a pharmacokinetic study of tacrolimus and everolimus in 8 maintenance renal patients with renal insufficiency that suggested no pharmacokinetic interactions between everolimus and tacrolimus when given simultaneously. CRAD001AUS09 was a prospective, multicenter, open-label, randomized, 6-month study of 92

de novo renal transplant patients. This study also included PK assessments, which demonstrated no interaction between everolimus and tacrolimus. Patients received concentration-controlled everolimus, corticosteroids, and basiliximab with low exposure tacrolimus or standard exposure tacrolimus. Everolimus trough levels were to be maintained above 3ng/mL. Despite the reduction in tacrolimus exposure, the immunosuppressive regimen was associated with low BPAR rates in both study groups and an excellent graft function. The combination of everolimus and tacrolimus was found to be safe and well tolerated with no unanticipated safety issues.

Further evidence of the effectiveness of de novo everolimus in combination with tacrolimus was gained in the CRAD001A2426 (ASSET) study. ASSET was designed to determine whether concentration-controlled everolimus plus reduced exposure tacrolimus can preserve renal function in 199 de novo renal recipients. From the study, the authors concluded that use of EVR 1.5mg bid in combination with low or very low TAC was associated with a low rate of tissue regeneration complications (lymphocele, wound complications, wound dehiscence or incisional hernia) in both groups. At Month 12, mean eGFR was higher in the tacrolimus 1.5-3 ng/ml group versus the 4-7 ng/ml group (57.1 ± 19.5 vs. 51.7 ± 20 ml/min/1.73 m2, respectively. Efficacy outcomes were similar in both study groups (Langer 2012).

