3.5 Purpose and timing of interim analyses/design adaptations

There will be a futility analysis when approximately 30% of subjects have completed 6 months on study. The primary analysis will be performed when the last subject completes 12 months on study. There will be a second analysis when the last subject completes 24 months on study to evaluate longer term outcomes.

Risks and benefits 3.6

In kidney transplantation there is a medical need for alternative immunosuppressive regimens which maintain the ability to prevent acute rejection while preserving renal function. A regimen that will maintain efficacy while allowing reduced CNI exposure to minimize or avoid CNIassociated adverse reactions (including nephrotoxicity) remains highly attractive.

Early renal transplantation studies using everolimus fixed doses with standard CNIs (CsA) exposure were associated with progressive deterioration of kidney function. This risk was addressed successfully when concentration controlled everolimus (3-8 ng/mL) was used with basiliximab induction and reduced exposure to CsA (Study CRAD001A2309, Tedesco 2010). The recently completed liver transplantation study (CRAD001H2304) also demonstrated that everolimus, in combination with reduced tacrolimus exposure and corticosteroids, showed

comparable efficacy and superior renal function versus the approved standard exposure tacrolimus at 12 months post liver transplantation (DeSimone 2012).

Everolimus, like all immunosuppressants, is associated with side effects. These effects are predominantly class-specific and well described; they are usually dose-related and prior experience has supported the value of therapeutic drug monitoring (TDM) for managing everolimus, similar to CNIs.

Overall, the safety findings in study CRAD001A2309 were consistent with the known safety profile of both everolimus and cyclosporine;

- Similar efficacy (tBPAR) compared to MPA plus standard cyclosporine control.
- Similar subject and graft survival compared to MPA plus standard cyclosporine control.
- Similar eGFR at Month 12 compared to MPA plus standard cyclosporine control.
- Increased incidence (more than 5% difference vs control) of hyperlipidemia, peripheral edema, dyslipidemia and stomatitis/mouth ulcerations with everolimus, these events being generally manageable in clinical practice.

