### 2.8.2 Safety Events of Interest

Safety events of interest, such as risks defined in the Safety Profiling Plan, Risk Management Plan or events of interest regarding signal detection or routine analysis are defined in the Program Case Retrieval Sheet (CRS) that is stored in CREDI at the path Cabinets/CREDI Projects/R/RAD001A/Integrated Medical Safety.

The following safety events of interest will be summarized with the number and percentage of patients experiencing the events, together with risk ratios (RRs) and 95% CIs. The version of the Case Retrieval Sheet used for the analyses will be described in a footnote. This includes MedDRA version and NMQ (Novartis MedDRA Queries) dictionary date.

- Anemia: Haematopoietic erythropenia (SMQ, broad search)

- Gastrointestinal ulcers: Gastrointestinal ulceration (SMQ, narrow search)  
This is a sub-SMQ under "Gastrointestinal perforation, ulceration, haemorrhage or obstruction (SMQ – narrow search)"
- Interstitial lung disease (CRS)
- Hyperlipidemia (CRS)
- Major cardiovascular events: Ischaemic heart disease and Cardiac failure (SMQ narrow search)
- Malignancy (CRS)
- NODM (See [Section 2.8.3.3](#))
- Peripheral edema (CRS)
- Proteinuria (associated chronic kidney disease) (CRS)
- Pleural effusion: MedDRA preferred term "Pleural effusion"
- Renal failure, excluding proteinuria (CRS)
- Stomatitis/mouth ulceration (CRS)
- Thrombocytopenia: Haematopoietic thrombocytopenia (SMQ, narrow search)
- Thrombotic and thromboembolic events: Embolic and thrombotic events (SMQ)
- Thrombotic microangiopathy (CRS)
- Wound healing events/disorders or complications: See [Section 4.4.1](#).

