### 2.8.3 Program Specific Safety Risk Events

The following program specific safety risk events as defined in the Program CRS will be summarized with the number and percentage of patients experiencing the events, together with risk ratios (RRs) and 95% CIs.

- Angioedema
- Chronic allograft nephropathy
- Edema (including peripheral edema)
- Everolimus and calcineurin inhibitor (CNI) induced renal dysfunction
- Exposure in pregnancy/breast-feeding women
- Hyperlipidemia
- Impaired male fertility
- Infections
- Infections (Polyomavirus infection)
- Interstitial lung disease
- Leukopenia and pancytopenia
- Malignancy
- New onset diabetes mellitus (NODM)
- Proteinuria (AE based definition)
- Proteinuria (lab based definition)
- Renal graft thrombosis
- Stomatitis and Mouth ulceration
- Teratogenicity

- Thrombotic microangiopathies (TMA)
- Venous thrombosis
- Wound-healing complications

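### The wound-healing event of interest in SAP 4.4.1 omits lymphocele and incisional hernia, which protocol 1.1 groups with wound complications, so its risk ratio cannot reflect them

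*SAP*

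**What the plan says.** SAP 2.8.2 (Safety Events of Interest) asks for patient counts, percentages, risk ratios and 95% CIs for a set of named events. Several are defined by the Program Case Retrieval Sheet (CRS), but wound healing is sent elsewhere: "Wound healing events/disorders or complications: See" SAP 4.4.1. That section opens with "The events of interest will be defined using MedDRA preferred terms or SMQs as follows" and gives 45 preferred terms, then the high level term Healing abnormal NEC with two further named terms.

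SAP 2.8.3 (Program Specific Safety Risk Events) lists "Wound-healing complications" again, also with risk ratios and 95% CIs, this time as defined in the Program CRS. The content of the CRS is not in the documents.

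Protocol 1.1 describes an earlier study that compared two levels of tacrolimus exposure, and reports a "low rate of tissue regeneration complications (lymphocele, wound complications, wound dehiscence or incisional hernia) in both groups". Everolimus was given in each of them; the regimen is described as "use of EVR 1.5mg bid in combination with low or very low TAC". The same section says that the lowest rates of several outcomes, including "wound healing events, peripheral edema, new-onset diabetes mellitus, hypercholesterolemia and hypertriglyceridemia were generally observed with everolimus trough concentration in the range 3–8 ng/mL".

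**The concern.** The protocol presents four surgical complications as one family in an everolimus setting. The SAP's visible wound-healing definition picks up two of them. The list is not confined to severe events, so a patient with an itching incision is a wound-healing case, while a patient with a lymphocele or an incisional hernia and no listed term is not. The SAP gives no reason for drawing the line there.

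Everolimus is started within 24 hours of transplantation (protocol 5.5.4), so readers will look to this line for the between-arm comparison of surgical-site healing. If the arms differ in lymphocele or incisional hernia, that line cannot show it. One risk is also measured by two definitions in the same report, with nothing said about how they relate.

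**Working it through.** The documents give no rates for these events, so there is no plan figure to reproduce. The check is a comparison of the passages, followed by an illustration on assumed rates.

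**Step 1: coverage of the protocol's grouping.** The 47 named terms (45 + 2) in SAP 4.4.1 were searched for each complication named in protocol 1.1.

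| Complication in protocol 1.1 | Matching terms in SAP 4.4.1 |
|---|---|
| Wound complications | 2 (Wound complication; Postoperative wound complication) |
| Wound dehiscence | 2 (Wound dehiscence; Abdominal wound dehiscence) |
| Lymphocele | 0 |
| Incisional hernia | 0 |

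Coverage is 2 of 4. The two terms named under Healing abnormal NEC are Excessive granulation tissue and Impaired healing, which do not change this.

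**Step 2: where else the omitted events could appear.**
- SAP 2.8.1 tabulates all adverse events by system organ class and preferred term, so each event would be counted. No risk ratio or CI is specified for those tables, and separate rows do not give the number of patients with any event of the family.
- SAP 2.8.1 also plans summaries by standardised MedDRA query with relative risks. The documents do not say whether lymphocele or incisional hernia falls under any such query.
- The SAP 2.8.3 line may include them, but its definition cannot be checked.

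**Step 3: possible effect on the risk ratio (all rates assumed).** Let c be the control-arm rate of listed events with ratio RR1, and a the control-arm rate of omitted events, in other patients, with ratio RR2.

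Broad RR = (c × RR1 + a × RR2) / (c + a)

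- c = 8%, RR1 = 1.00, a = 2%, RR2 = 1.25: (0.080 + 0.025) / 0.10 = 1.05. Excess outside the list: 1020 × 0.02 × 0.25 ≈ 5 patients per arm of 1020.
- c = 8%, RR1 = 1.00, a = 8%, RR2 = 2.00: (0.08 + 0.16) / 0.16 = 1.50. Excess outside the list: 1020 × 0.08 × 1.00 ≈ 82 patients.
- RR1 = RR2 = 1.25: the broad RR is also 1.25, and only the event count changes.
- Listed 18% v 12% (RR 1.50), omitted 5% v 5%: 23% / 17% = 1.35. Here adding the terms lowers the ratio.

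The list-only ratio can thus lie below, at or above the broader one, depending on rates that the documents do not give.

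**The case against.** The strongest reply is that nothing in the documents makes lymphocele or incisional hernia an expected everolimus harm. A reader might infer that the list hides a known excess in the everolimus arm. The documents do not support that. The study in protocol 1.1 reports a low rate, and both of its groups received everolimus, so it offers no contrast with MPA. Protocol 3.6 states what rose against an MPA control, "Increased incidence (more than 5% difference vs control) of hyperlipidemia, peripheral edema, dyslipidemia and stomatitis/mouth ulcerations with everolimus", and names no wound event, lymphocele or hernia. Only wound healing events in general are tied to everolimus exposure. This part of the reply stands in full.

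A reader might also infer that the omission pulls the risk ratio toward 1. The last two illustrations show that it need not, so that reading fails too.

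The protocol's label is tissue regeneration complications, a wider term than wound healing, and it lists wound complications beside lymphocele and hernia, not above them. A narrower list may therefore be deliberate. That is a fair reading, but the SAP does not say so.

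Finally, the events are not lost: they are tabulated by preferred term, serious ones are reported whether on or off treatment, and the CRS definition may already include them. That limits the point without removing it. The preferred-term tables carry no stated risk ratio and no patient count for the combined family, and an unseen definition cannot be relied on. Nor does the unseen CRS prove a conflict between 2.8.2 and 2.8.3; it shows only two sources for one risk, with their relation unstated.

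**Conclusion.** The point holds as a gap in definition. The SAP 2.8.2 risk ratio and CI for wound healing cannot reflect any between-arm difference in lymphocele or incisional hernia, two of the four complications that the protocol groups together. On what the documents show, a ratio and CI covering them is assured nowhere else; it would depend on the CRS definition or a standardised query happening to include them.

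The direction and size of any effect on the reported ratio are unknown, and the figures above are illustrations only. No excess over MPA should be presumed. Wound healing is not among the safety outcomes named in the protocol's objectives, and the primary and key secondary analyses are unaffected. This is a cheap improvement.

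**What to change.** Add lymphocele and incisional hernia to SAP 4.4.1. Report n, %, risk ratio and 95% CI for each as its own line and for a combined total, and keep the existing list-only line beside them. Showing the lines separately means that neither set of terms can mask the other. State where the 4.4.1 list and the CRS definition used in 2.8.3 differ. Seroma and other postoperative hernia terms are optional, because neither document mentions them.

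The cost is a few terms and a few more output lines. Adverse events are already coded to preferred terms, so no new data are needed. The combined total may look less favourable to everolimus than the list-only line.

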## 4.5 Renal Variables

### 4.5.1 eGFR Using MDRD 4

Estimated GFR using the MDRD formula is based on serum creatinine, age, race and gender. The MDRD formula is:

$$\text{eGFR-MDRD4 [mL/min/1.73m}^2] = 186.3 * (C^{-1.154}) * (A^{-0.203}) * G * R;$$

where C is the serum concentration of creatinine (mg/dL), A is age (years), G=0.742 when gender is female or G=1 if gender is male, and R=1.21 when race is black or R=1 otherwise.

### 4.5.2 eGFR Using Hoek Formula on Cystatin C

Estimated GFR using the Hoek formula based on Cystatin C:

$$\text{eGFR-Hoek [mL/min/1.73m}^2] = -4.32 + 80.35 * 1/C;$$

where C = Cystatin C in mg/L.

### 4.5.3 eGFR Using CKD EPI Formula

$$\text{eGFR-CKDEPI [mL/min/1.73m}^2] = 141 * \min(C/\kappa, 1)^\alpha * \max(C/\kappa, 1)^{-1.209} * 0.993^{\text{Age}} * 1.018 \text{ [if female]} * 1.159 \text{ [if black];}$$

Where C is serum creatinine (mg/dL),  $\kappa$  is 0.7 for females and 0.9 for males,  $\alpha$  is -0.329 for females and -0.411 for males, min indicates the minimum of C/ $\kappa$  or 1, and max indicates the maximum of C/ $\kappa$  or 1.

## 4.6 Clinically Notable Laboratory and Vital Signs Abnormality Criteria/Levels

### 4.6.1 Clinically notable laboratory abnormality criteria/levels

Laboratory variable	Standard units	SI units
Liver function and related variables		
SGOT (ASAT)	$\geq 3 \times \text{ULN}$	$\geq 3 \times \text{ULN}$
SGPT (ALAT)	$\geq 3 \times \text{ULN}$	$\geq 3 \times \text{ULN}$
Bilirubin	$\geq 3 \times \text{ULN}$	$\geq 3 \times \text{ULN}$
Renal function, metabolic and electrolyte variables		
Urea	$\geq 5 \times \text{ULN}$	$\geq 5 \times \text{ULN}$
Uric acid	M $\geq 12 \text{ mg/dL}$ F $\geq 9 \text{ mg/dL}$	M $\geq 714 \mu\text{mol/L}$ F $\geq 535 \mu\text{mol/L}$
Glucose	$< 45 \text{ mg/dL}$ $> 250 \text{ mg/dL}$	$< 2.5 \text{ mmol/L}$ $> 13.9 \text{ mmol/L}$
CK (MB)	None	None
Potassium	$\leq 3.0 \text{ mEq/L}$	$\leq 3 \text{ mmol/L}$

	≥6.0 mEq/L	≥6 mmol/L
Calcium	≤6 mg/dL	≤1.5 mmol/L
	≥13 mg/dL	≥3.2 mmol/L
Hematology variables		
Hemoglobin	<7 g/dL	<4.39 mmol/L
Platelets (thrombocytes)	<50 k/mm 	<50 × 10  /L
	≥700 k/mm 	≥700 × 10  /L
Leukocytes (WBCs)	≤2.0 k/mm 	≤ 2.0 × 10  /L
	≥16 k/mm 	≥16 × 10  /L
Hematology variables: differential		
Granulocytes (poly, neutrophils)	≤1,000/mm 	≤1 × 10  /L
Eosinophils	≥12%	≥12%
Lymphocytes	≤1,000/mm 	≤1 × 10  /L

#### 4.6.2 Clinically notable vital signs abnormality criteria/levels

Vital sign variables	Notable criteria
Systolic BP (mm/Hg)	Either an increase of ≥30 that results in ≥180 or >200(mm/Hg) OR a decrease of ≥30 that results in ≤90 or <75 (mm/Hg)
Diastolic BP (mm/Hg)	Either an increase of ≥20 that results in ≥105 or >115 (mm/Hg) OR a decrease of ≥20 that results in ≤50 or <40 (mm/Hg)

### 4.7 Statistical Models

#### 4.7.1 Dummy Codes for Estimating Event Rate, Event Rate Difference and Respective 95% CI as Well as No-Difference Testing for The Composite Endpoint of tBPAR or eGFR < 50 mL/min/1.73m^2

As described in [Section 4.2.1](#), multiple imputation, and control-based imputation will be applied to the primary and sensitivity analyses for the composite endpoint of tBPAR or eGFR < 50 mL/min/1.73m^2. For the component of eGFR < 50 mL/min/1.73m^2, a value for missing eGFR as a continuous variable will be imputed first, then dichotomized it to derive this endpoint.

To estimate event rate, event rate difference and respective 95% CI as well as no-difference testing for tBPAR or eGFR < 50 mL/min/1.73m^2, the following dummy SAS codes can be adapted:

```

*** Use multiple imputation, or control-based imputation method to impute a value for
missing eGFR as a continuous variable;
*** Dichotomized imputed eGFR to derive the endpoint of eGFR < 50 mL/min/1.73m2;
*** Derive the composite endpoint of tBPAR or eGFR < 50 mL/min/1.73m2;
*** Assume the dataset imp_data contains the variable EVENT (event=1 if composite
endpoint of tBPAR or eGFR < 50 mL/min/1.73m2 occurred; =0 otherwise) for each of
of the imputations;

```

```

PROC sort data=imp_data;
  by _imputation_;

```

```
run;

ods output RiskDiffCol2=diff;
proc freq data=imp_data;
  by _imputation_;
  tables trt*event/riskdiff;
run;

*** diff dataset contains the following:

Obs    _Imputation_    Row          Risk          ASE
-----
1       1                Row 1         0.3623        0.0289
2       1                Row 2         0.4729        0.0300
3       1                Total         0.4177        0.0210
4       1                Difference    -0.1106       0.0417
5       2                Row 1         0.3732        0.0291
6       2                Row 2         0.4874        0.0300
7       2                Total         0.4304        0.0211
8       2                Difference    -0.1142       0.0418
... ..

*** Event rate and 95% CI in Treatment1;
proc mianalyze data=diff(where=(row='Row 1'));
  modeleffects risk;
  stderr ASE;
run;

*** Event rate and 95% CI in Treatment2;
proc mianalyze data=diff(where=(row='Row 2'));
  modeleffects risk;
  stderr ASE;
run;

*** Difference in event rate and 95% CI for 'Treatment1 -
Treatment2';
*** P-value for the no-difference test;
proc mianalyze data=diff(where=(row='Difference'));
  modeleffects risk;
  stderr ASE;
run;
```

